13.2 Sample Size, Accrual Rate and Study Duration

Accrual of up to 20 patients may be required to achieve 18 evaluable patients.

The primary endpoint is the rate of overall survival at 3 months (OS3). Any patient whose vital status at 3 months cannot be determined will be counted as having died. A Simon two-stage design will be used to compare a null hypothesis OS3 of 18% against an alternative of 43%. Nine patients will be enrolled in the first stage. If 0 or 1 patients are alive at 3 months, the trial will be stopped early. If 2 or more patients are alive at 3 months, we will enroll an additional 9 patients. If at least 6 patients among the total of 18 patients are alive at 3 months, then the treatment would be promising in the cohort. This design has a type-I error of 8% (target 10%) and power of 86% (target 85%). If the null hypothesis is true, then the probability is 0.50 of stopping at the end of the first stage.

In addition, we will assess for the primary outcome of any histologic, molecular subtype (e.g., ER/PR-positive, HER2-positive breast cancer, EGFR mutant lung cancer) with 6 patients

enrolled for that particular subtype. If no patient within a particular histologic subtype has achieved the primary outcome, then patients with that histology will no longer be eligible to enroll in the trial. Under the alternative hypothesis (i.e., OS3 = 43%), the probability is 0.03 of observing no patients with OS3 among 6 patients.

The accrual rate is based on our institutional patient volume of 3-4 patients per month with leptomeningeal carcinomatosis seen in our multidisciplinary brain metastasis clinic. We estimate that 1-2 patients per month will be eligible for this protocol. Therefore, 20 patients will be accrued within 10-20 months. Based on six months of follow-up (median survival of patients is approximately 2-4 months), total study duration will be 24 months.

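### The two-stage design as written has 84.2% power, not the stated 86%, and falls just short of its own 85% target

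*Combined protocol and SAP*

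**What the plan says.** Section 13.2 (Sample Size, Accrual Rate and Study Duration) defines the primary test completely. The endpoint is binary, alive or not at 3 months, and unknown vital status counts as death. The hypotheses are set by "A Simon two-stage design will be used to compare a null hypothesis OS3 of 18% against an alternative of 43" percent. The rules are:

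- Stage 1: "Nine patients will be enrolled in the first stage".
- Futility: "If 0 or 1 patients are alive at 3 months, the trial will be stopped early".
- Stage 2: "If 2 or more patients are alive at 3 months, we will enroll an additional 9 patients".
- Success: "If at least 6 patients among the total of 18 patients are alive at 3 months, then the treatment would be promising in the cohort".

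The section then gives the operating characteristics: "This design has a type-I error of 8% (target 10%) and power of 86% (target 85". It puts the probability of stopping after stage 1 under the null at 0.50. No method or software is named. Section 13.4 (Interim Monitoring Plan) reads N/A, and section 13.5 (Analysis of Primary Endpoints) gives no power figure, so nothing elsewhere corrects the statement.

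**The concern.** Three figures are quoted for one design: type-I error, power and early-stopping probability. They should all follow from the same exact binomial calculation. Two do. The power does not, and it errs in the favourable direction, turning a small miss of the target into an apparent small margin.

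What is at stake is the type-II error, the chance of discarding the combination when 3-month survival is truly 43%. The text implies 14% against a target of 15%; the design gives 15.8%. A reader weighing the futility rule is also not shown what it costs in power.

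**Working it through.** **Inputs, all from section 13.2.** p0 = 0.18, p1 = 0.43, n1 = 9, n2 = 9. Continue if X1 ≥ 2. Success if X1 + X2 ≥ 6.

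**Formulas.**

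- P(early stop | p) = P(X1 = 0) + P(X1 = 1), with X1 ~ Bin(9, p).
- P(success | p) = Σ over x = 2,…,9 of P(X1 = x) · P(X2 ≥ 6 − x), with X2 ~ Bin(9, p).

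The calculation is exact and uses no approximation.

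**The plan's own figures first, at p = 0.18.**

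- Early stop: 0.1676 + 0.3312 = 0.4988. Stated 0.50; agrees.
- Type-I error: 0.01789 (x = 2) + 0.03134 (x = 3) + 0.02458 (x = 4) + 0.00896 (x = 5) + 0.00174 (x ≥ 6) = 0.0845. Stated 8%; agrees.

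The agreement shows that the rules have been read as intended.

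**Power, at p = 0.43.**

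| Alive in stage 1 (x) | P(X1 = x) | P(X2 ≥ 6 − x) | Product |
|---|---|---|---|
| 2 | 0.13013 | 0.59135 | 0.07695 |
| 3 | 0.22905 | 0.82040 | 0.18791 |
| 4 | 0.25919 | 0.95053 | 0.24637 |
| 5 | 0.19553 | 0.99365 | 0.19429 |
| 6 to 9 | 0.13663 | 1 | 0.13663 |
| Sum | | | **0.8421** (from unrounded terms) |

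Power is 84.2% and type-II error 15.8%. The gap to the stated 86% is 1.8 points; the gap to the 85% target is 0.8 points.

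**Where 86% may come from.** With no interim look, P(Bin(18, 0.43) ≥ 6) = 0.8573, which rounds to 86%. The difference, 0.8573 − 0.8421 = 0.0152, is the probability at p = 0.43 that a trial has 0 or 1 alive among the first 9 but would have reached 6 of 18 had it continued. The total probability of stopping at stage 1 under the alternative is 0.0064 + 0.0431 = 0.0495. The same single-stage rule has type-I error P(Bin(18, 0.18) ≥ 6) = 0.0889, which rounds to 9%, not the stated 8%. So the three stated figures do not come from a single-stage reading either.

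**Can rounding of the 43% explain it?** Two-stage power across the values that round to 43%, and just above:

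| p1 | Power |
|---|---|
| 0.425 | 0.832 |
| 0.430 | 0.842 |
| 0.434 | 0.850 |
| 0.435 | 0.852 |
| 0.440 | 0.861 |

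Nothing that rounds to 43% gives 86%.

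**Other readings tried at p1 = 0.43.** Stopping only at 0 of 9 gives power 0.856, but type-I error 0.0886 and early stopping of 0.17 under the null. Applying the at-least-6 rule to all 20 patients the plan may accrue gives power 0.896 with type-I error 0.123. No reading tried yields 8%, 0.50 and 86% together.

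**The case against.** The strongest case on the other side accepts the arithmetic and disputes its weight.

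- **The gap is small.** It is 1.8 points against the stated figure and 0.8 against the target, and correcting it changes no decision rule. The stage sizes, stopping rule, success rule, type-I error and early-stopping probability are consistent with one another. This stands: it is an error of statement and does not by itself make the design unsound.
- **The miss of the 85% target is sensitive to rounding.** An unrounded alternative of about 0.434 would reach 0.850. This is true, but the plan prints 43% and nothing suggests another value was used. Rounding in any case cannot rescue the stated 86%.
- **The single-stage explanation is an inference.** This also stands, because the documents name no method. The mismatch does not depend on how it arose.
- **A redesign is not required.** Where survival is this short, a sponsor may reasonably prefer the higher chance of stopping early for an inactive regimen and accept 84% power. This stands, and is why restating the figure is enough.

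**Conclusion.** The stated power is wrong. At the plan's own 43% alternative the design has 84.2% power: 1.8 points below the 86% claimed and 0.8 points below the 85% target. Type-II error is 15.8%, against 14% implied and 15% targeted. The type-I error and early-stopping statements are correct.

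The result assumes only that 43% means 0.43, that 18 patients enter the decision, and that outcomes are independent with a common probability, as the two-stage binomial design itself assumes. Counting patients of unknown vital status as dead can only lower the achieved power. The text should be corrected because it is the primary design statement and it claims that a target is met when it is not; the practical effect is modest.

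**What to change.** **Sufficient change.** In section 13.2, give power as 84% and say that this is slightly below the 85% target. Type-I error (8%) and early stopping under the null (0.50) stay as they are. This costs nothing beyond a less favourable figure.

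**Optional, if 85% must be met with 18 patients.** Enrol 10 in stage 1 and 8 in stage 2, keeping the stop at 0 or 1 alive and success at 6 or more of 18. Exact results:

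| | 9 + 9 | 10 + 8 |
|---|---|---|
| Type-I error | 8.45% | 8.7% |
| Power at 43% | 84.2% | 85.1% |
| Early stop under the null | 0.499 | 0.439 |
| Expected N under the null | 9 + 0.501 × 9 = 13.5 | 10 + 0.561 × 8 = 14.5 |

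This clears the target by only 0.1 point. It costs one more first-stage patient, a lower chance of stopping an inactive regimen early, and about one more patient on average under the null. Whichever option is chosen, the section should state that the figures are exact two-stage binomial values so that they can be reproduced together.

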13.3 Stratification Factors

N/A

13.4 Interim Monitoring Plan

N/A

13.5 Analysis of Primary Endpoints

The primary endpoint is the rate of overall survival at 3 months (OS3). Any patient whose vital status is unknown due to loss of follow-up will be classified as having died for purposes of estimating the primary endpoint. The proportion of patients alive at 3 months will be summarized with a 90% confidence interval estimated using the method of Atkinson and Brown, which allows for the two-stage design. Based on a sample of 18 patients, the confidence interval will be no wider than 0.42.

13.6 Analysis of Secondary Endpoints

Safety and Tolerability: All adverse events recorded during the trial will be summarized for all patients having received one or more doses of ipilimumab and nivolumab. The data for each cohort will be summarized separately, although safety data may be combined, if appropriate. The proportions of patients with grade-3 or higher hematologic toxicities or grade-3 or higher neurologic toxicities will be presented with 90% exact binomial confidence intervals. The incidence of events that are new or worsening from the time of first dose of treatment will be summarized according to system organ class and/or preferred term, severity (based on CTCAE grade), type of adverse event, and relation to study treatment. Deaths reportable as SAEs and non-fatal serious adverse events will be listed by patient and tabulated by primary system organ class, and type of adverse event.

Intracranial/Extracranial Response: The proportion of patients with intracranial response of intraparenchymal brain metastases (CR or PR by RANO) will be presented with a two-sided, 90% exact binomial confidence interval. For a sample of 18 patients, the confidence interval will have maximum width of 0.42. Extracranial response rates (CR or PR) according to RECIST and irRC will be summarized. Rates will be accompanied by two-sided 90% exact binomial

confidence intervals. Cases where RECIST and irRC responses do not agree will be documented.

Leptomeningeal Disease Response: The proportion of patients with leptomeningeal disease response (CR or PR) will be presented with a two-sided, 90% exact binomial confidence interval. For a sample of 18 patients, the confidence interval will have maximum width of 0.42.

Extracranial PFS and Intracranial PFS: Extracranial PFS (EPFS) is defined as the time from first dose of study drug to documented extracranial progression (per RECIST or irRC) or death, whichever occurs first. Intracranial PFS (IPFS) is defined as the time from first dose of ipilimumab and nivolumab to documented intracranial progression (RANO) or death, whichever occurs first. For both endpoints, the follow-up of patients who have neither died nor progressed at the time of analysis will be censored at the date of last adequate disease assessment. Each cohort will be presented separately. Median EPFS and IPFS will be presented and accompanied by 90% confidence intervals estimated using log(-log(survival)) methodology. Point estimates at 3 and 6 months will also be presented with confidence intervals.

13.7 Analysis of Exploratory Endpoints

Biomarkers of blood and tissue: Analyses of blood and tissue biomarkers will be based on descriptive statistics, as appropriate for the biomarker.

To examine response according to pre-treatment levels of biomarkers, the study sample will be divided retrospectively according to the primary endpoint of response or non-response. Pre-treatment biomarker levels will be summarized descriptively for the two response groups and compared using Wilcoxon rank-sum tests for markers measured on a continuous scale, or Fisher's exact tests for those measured on a categorical scale. Where appropriate, visualization of the relationship between baseline marker levels and the distributions of PFS or OS will employ Kaplan-Meier estimates stratified by biomarker levels. Medians of the time-to-event endpoints will be shown with two-sided 90% confidence intervals; the distributions of PFS and OS will be compared across biomarker strata using the log-rank test.

Changes in biomarkers between pretreatment and progression or treatment discontinuation will be calculated (post-pre) for each patient and summarized descriptively. In addition, the correlation of changes in tissue biomarkers with changes in measures of peripheral blood markers will be explored graphically, or by appropriate statistical methods based on data availability, to assess associations.

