13.1 Study Design/Endpoints

Primary endpoint: Rate of overall survival at 3 months

Secondary Endpoints:

1. Toxicity by CTCAE criteria (grade 3 or higher hematologic toxicity; grade 3 or higher neurologic toxicity)
2. Intracranial response in patients with leptomeningeal metastases
3. Extracranial response as determined by RECIST and irRC
4. Leptomeningeal disease response as defined in section 11.4
5. Time to the first occurrence of extracranial disease progression, or death from any cause
6. Time to the first occurrence of intracranial disease progression, or death from any cause

Exploratory Endpoints: Genetic alterations

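### Section 13.7 tests PFS and OS only across biomarker strata and gives no cut-point rule, so a continuous marker has to be cut and the choice of cut is left open

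*Combined protocol and SAP*

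**What the plan says.** Section 13.7 opens by saying that "Analyses of blood and tissue biomarkers will be based on descriptive statistics, as appropriate for the biomarker". It then sets out two kinds of comparison for pre-treatment markers.

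- **Response groups.** Responders and non-responders are compared with "Wilcoxon rank-sum tests for markers measured on a continuous scale, or Fisher's exact tests for those measured on a categorical scale". Continuous markers are therefore expected, and here they stay uncut.
- **PFS and OS.** The relevant sentence begins "Where appropriate, visualization of the relationship between baseline marker levels and the distributions of PFS or OS" and says that this "will employ Kaplan-Meier estimates stratified by biomarker levels". Medians get two-sided 90% confidence intervals, and "the distributions of PFS and OS will be compared across biomarker strata using the log-rank test".

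The section gives no number of strata, cut-point, rule for choosing a cut, significance level, or regression on the uncut marker. Section 13.1 lists "Exploratory Endpoints: Genetic alterations" as the only exploratory endpoint. Section 9.2, however, also plans cytokine arrays, mass-spectrometry protein quantification and transcript expression, which are naturally continuous.

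**The concern.** A log-rank test needs groups. For a continuous marker, the analyst must choose a cut before the one stated survival test can be run. Two things follow.

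1. With no rule in the plan, the cut can be chosen after looking at the curves. A nominal p-value from a chosen cut does not have its nominal error rate.
2. Even a cut fixed in advance treats all patients on the same side as equal. If the hazard changes gradually with the marker, information is thrown away in a sample that is already very small.

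The Wilcoxon comparison does not fill the gap, because its outcome is a two-group classification. No planned test uses both the uncut marker and the survival time.

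At stake is how far a reported association between a CSF or blood marker and PFS or OS can be believed, and how likely a real graded association is to be detected.

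**Working it through.** **No figure in the plan to reproduce.** The documents give no power, marker effect or significance level for these tests. The sample size of 18 comes from the two-stage design in section 13.2. Its stated probability of early stopping under the null reproduces: 0.82^9 + 9 × 0.18 × 0.82^8 = 0.168 + 0.331 = 0.499 (stated 0.50).

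**Inputs from the documents.**
- 18 evaluable patients (13.2).
- Median survival about 2-4 months, with 3 used, and six months of follow-up (13.2).
- Survival calls for up to two years after protocol therapy (5.6), so nearly all OS events could be observed.

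**Assumptions, because the documents are silent.**
- Standard normal marker x with hazard λ·exp(βx), where exp(β) is the HR per SD, varied from 1.25 to 3.0.
- Exponential survival.
- Two-sided 5%, and also 10%, which the 90% intervals in 13.7 suggest.

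**Tests compared.** The Cox score statistic is Z = U/√V. U sums, over events, the marker value minus its mean in the risk set. V sums the risk-set variances. The log-rank test is the same statistic with x replaced by a 0/1 indicator for above or below the median.

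**Hand check of the mechanism.** The two halves of a normal marker differ in mean by 2√(2/π) = 1.596 SD. With D events, the expected Z is about √D·ln(HR) uncut and √D·√(2/π)·ln(HR) after the split, that is 0.798 times as large. For D = 18 and HR 2.0:
- uncut: 4.243 × 0.693 = 2.941, power Φ(2.941 − 1.960) = 83.7%
- split: 2.941 × 0.798 = 2.346, power Φ(2.346 − 1.960) = 65.0%

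This approximation overstates both powers in so small a sample, so simulation is used for the results.

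**Simulated power, n = 18, 20,000 trials per setting, all events observed, two-sided 5%.**

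| HR per SD | Cox, uncut | Log-rank, median split | Loss (points) |
|---|---|---|---|
| 1.5 | 31.7% | 23.1% | 8.6 |
| 1.75 | 51.6% | 35.2% | 16.4 |
| 2.0 | 66.2% | 46.3% | 19.9 |
| 2.5 | 84.6% | 63.2% | 21.4 |

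- With six months of follow-up, the loss over HR 1.5-2.5 is 7.8 to 22.4 points.
- At two-sided 10%, it is 10 to 19 points over the same range.
- At HR 1.25 the loss is 2-3 points. At HR 3.0 it is 12-23 points, depending on follow-up and significance level.
- Tertiles give power within about 1-3 points of the median split.
- Under the null at nominal 5% with all events, the uncut test rejects in 5.9% of trials and the pre-set median split in 6.5%.

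**If the effect is a step at the median instead (5%, all events).** With a between-group HR of 3, the split has 56.4% power and the uncut test 34.8%. The ordering reverses.

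**If the cut is chosen from the data.** Under the null, taking the cut with the largest statistic, with at least about 4 patients on each side, gives false-positive rates of about 27-30% at nominal 5% and about 44-48% at nominal 10%. This result needs no assumption about the marker effect.

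**The case against.** The strongest reply has four parts.

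- **The text does not promise to cut every continuous marker.** The stratified curves are a visualisation to be used where appropriate, the section is framed as descriptive, and the only named exploratory endpoint is genetic alterations, for which strata are natural categories. This stands in part. For mutation status the log-rank test is suitable and nothing needs changing. But the log-rank clause carries no such qualifier, and it is the only survival test offered for any marker.
- **A power loss of a fixed size is not a property of this plan.** This stands. A reader might infer that stratifying costs roughly 20 points as a matter of fact. The documents give no effect size, effect shape or significance level, and a threshold effect reverses the comparison.
- **Pre-specifying the median would control the error rate without changing the test.** This stands, as the null results show. It would not recover the power lost under a graded effect.
- **The stakes are low.** This stands. No decision, power target or significance level is attached. Even the uncut test has only 66.2% power at HR 2.0 per SD.

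A reader might also infer that the correlative objective in section 1.4 depends on this test. It does not: that objective concerns biomarkers of response, and the responder comparison already keeps continuous markers uncut.

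**Conclusion.** The point holds as a minor improvement to an exploratory analysis. The firmer half is the missing cut-point rule, because the inflation to about 27-30% (nominal 5%) or 44-48% (nominal 10%) depends only on the cut being searched for at n = 18. The plan does not say that such a search will be made; it simply does nothing to prevent one.

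The power half is conditional. With a log-linear effect, a median split and two-sided 5%, the loss is about 2-3 points at HR per SD 1.25 and about 8-23 points at 1.5-2.5. With a step at the median there is no loss but a gain. The primary endpoint, the stopping rule and the secondary endpoints are untouched.

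**What to change.** Replace the log-rank sentence in section 13.7 with:

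> For continuous markers, association with PFS and OS will be tested by the score test from a Cox model with the rank (normal-score) transformed marker as a continuous covariate, reporting the hazard ratio per SD with a 90% CI. Kaplan-Meier curves split at the sample median are for display only. The log-rank test is used for categorical markers.

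Naming one transformation closes off a further analyst choice, and in simulation it kept almost all the power of the untransformed test under a graded effect. If the team prefers to keep the log-rank test throughout, fixing the cut at the sample median in advance is the least that is needed.

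The cost is a few lines of text, with no extra data or patients. The downside is some loss of power if the true effect is a threshold. The change does not deal with multiplicity across the many markers planned in section 9.2; that would need its own statement.

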1.4 Correlative Objectives

1. To determine molecular biomarkers of response using next generation sequencing techniques.

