Cell Purification by Flow Cytometry: CSF will be sorted on CD45 to separate tumor (CD45-) and immune (CD45+) cells for genomic and transcriptomic analyses. CD4⁺ and CD8⁺ T cells and myeloid cells (CD11b⁺) will be purified from the CSF and PBMC by flow cytometry and processed for transcriptome sequencing. We will systematically assess differentially expressed transcripts in pre- and on- treatment samples to determine if there is enrichment within particular gene pathways (such as exhaustion, anergy, senescence) through GeneSet Enrichment Analysis (GSEA) and gene co-expression network analysis.

Cytokine and Proteomic Analyses: We will analyze cytokines in CSF and serum using cytokine bead arrays. High-resolution mass spectrometers and isobaric tandem mass tags will be used to quantify proteins from CSF and serum samples. The tandem mass tag technology allows for the analysis of 6-10 samples within a single experiment. For example, protein expression can be profiled after nine treatment conditions and compared to an untreated sample across >6,000 proteins. All mass spectrometry data will be analyzed in partnership with the Thermo Fisher Scientific Center for Multiplexed Proteomics at Harvard Medical School.

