^h: Off-study evaluation: End of treatment assessments to be performed within 7 days after last day drug administration or within 7 days after decision to end treatment. Assessments may continue for ongoing reportable adverse events. In participants who discontinue study treatment without documented disease

progression, every effort should be made to continue monitoring their disease status by radiologic imaging every 6 weeks (+/- 7 days) until (1) the start of new anti-cancer treatment, (2) documented disease progression, (3) death or (4) the end of the study, whichever occurs first

ⁱ: Follow-up visit 1 = 30 days from the last dose +/- 7 days or coincide with the date of discontinuation (+/- 7 days) if date of discontinuation is greater than 37 days after last dose, Follow-up visit 2 (FU2) = 8-10 weeks (+/- 7 days) from follow-up visit 1. After 2 followup visits, patients will be followed with a phone call every 10-12 weeks for survival information.

^jBlood will be collected at screening, Day 1, then every 3 weeks during the induction phase and every 4 weeks during the maintenance phase (two 10 mL EDTA/lavender top tube) and at the end of treatment

Calendar During Maintenance Phase for Melanoma, Small Cell Lung Cancer, Breast Cancer, Bladder Cancer, Renal Cancer and other Solid Tumors

	Wk	Wk	Wk	Wk	Wk	Wk	Wk	Wk	Wk	Wk	Wk	Wk	Off Treatment	Follow-up visits ⁱ
	13	14	15	16	17	18	19	20	21	22	23	24		
	To be repeated beyond 24 weeks until patient goes off study													
Nivolumab (for melanoma and renal cell carcinoma)	B			B					B					
Nivolumab (for small cell lung cancer, breast cancer and bladder cancer)	C		C	C		C		C			C			
Concurrent meds	X-----X													
Physical exam ^b	X		X		X		X		X		X		X	X
Vital signs	X		X		X		X		X		X		X	X
Height														
Weight	X		X		X		X		X		X		X	X
Performance status	X		X		X		X		X		X		X	X
CBC w/diff, plts	X		X		X		X		X		X		X	X
Serum chemistry ^c	X		X		X		X		X		X		X	X
EKG (as indicated) ^d														
Adverse event evaluation	X-----X												X	X
Tumor measurements	Tumor measurements are repeated every 8 weeks. Documentation (radiologic) must be provided for participants removed from study for progressive disease.												X	
Radiologic evaluation	Radiologic measurements should be performed every 8 weeks (Brain MRI and CT Chest/Abd/Pelvis)												X	X
B-HCG	X						X							X
Cerebrospinal fluid	X				X				X					
Blood ^j	X				X				X				X	X
Archival tissue ^g													X	X

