11.4 Other Response Parameters

Cerebrospinal Fluid: Cerebrospinal fluid will collected as part of clinical care.

Leptomeningeal response will be defined as below:

Response	Cytologic	Neurologic	Radiographic
Complete Response	Reversion to (-) CSF cytology (or NA)	Disappearance of all disease related symptoms present prior to therapy (or NA)	Complete disappearance of all detectable radiographic EOD (or NA)
Partial Response	> 50% decrease in malignant CSF cytology	Improvement in neurologic symptoms or no worsening of symptoms	Improvement in radiographic evidence of disease. No new sites of measurable or assessable CNS disease
Stable Disease	Not fulfilling the criteria for CR or PR, but not progressive disease	Not fulfilling the criteria for CR or PR, but not progressive disease	Not fulfilling the criteria for CR, or PR but is not progressive disease
Progressive Disease	> 50% increase in malignant CSF cytology	Development of new neurologic symptoms related to neoplastic meningitis	Increase in radiographic evidence of disease. Appearance of new sites of disease.

Leptomeningeal response will be a secondary outcome.

The immune related Response Criteria (irRC) will also be used in this study to support secondary efficacy endpoints for extracranial lesions. Definitions of the immune-related Response Criteria (irRC) are below and are presented in Appendix B:

- Complete Response (CR): Disappearance of all lesions in two consecutive observations not less than 4 wk apart
- Partial Response (PR): $\geq 50\%$ decrease in tumor burden compared with baseline in two observations at least 4 wk apart
- Stable Disease (SD): 50% decrease in tumor burden compared with baseline cannot be established nor 25% increase compared with nadir
- Progressive Disease (PD): At least 25% increase in tumor burden compared with nadir (at any single time point) in two consecutive observations at least 4 wk apart

Index Lesion	Non-Index Lesion	New Measurable Lesions	New unmeasurable lesions	% change in tumor burden	Overall IR Response
CR	CR	No	No	-100%	irCR
PR	Any	Any	Any	$\geq -50\%$	irPR
PR	Any	Any	Any	$< -50\% \text{ to } < 25\%$	irSD
PR	Any	Any	Any	$\geq +25\%$	irPD
SD	Any	Any	Any	$< -50\% \text{ to } < +25\%$	irSD
SD	Any	Any	Any	$\geq +25\%$	irPD
PD	Any	Any	Any	$\geq +25\%$	irPD

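### Section 13.7 splits patients by a response-type primary endpoint the trial does not have, and times biomarker change only at progression or discontinuation: the correlative objective is weakened, not defeated

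*Combined protocol and SAP*

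**What the plan says.** Correlative objective 1.4 is "To determine molecular biomarkers of response using next generation sequencing techniques".

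Section 13.7 opens with "Biomarkers of blood and tissue: Analyses of blood and tissue biomarkers will be based on descriptive statistics" and then sets out three pieces of work:

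- **Baseline comparison.** For this, "the study sample will be divided retrospectively according to the primary endpoint of response or non-response". The two groups are compared by Wilcoxon rank-sum or Fisher's exact test.
- **Baseline markers and time to event.** Kaplan-Meier curves and log-rank tests of PFS and OS across marker strata.
- **Change.** "Changes in biomarkers between pretreatment and progression or treatment discontinuation will be calculated (post-pre) for each patient and summarized descriptively". Tissue changes are then related to blood changes as far as the data allow.

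Other sections bear on this. Section 13.1 reads "Primary endpoint: Rate of overall survival at 3 months", and section 11.4 adds "Leptomeningeal response will be a secondary outcome". Section 9.2 plans a different contrast: "We will systematically assess differentially expressed transcripts in pre- and on- treatment samples". In section 10 the blood footnotes end with "two 10 mL EDTA/lavender top tube) and at the end of treatment"; the CSF footnotes have no such clause.

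**The concern.** Two pieces of 13.7 do not fit the rest of the protocol.

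The first is the grouping. It cites a primary endpoint and calls it response, and the trial has no endpoint that is both. Because the division is made retrospectively, the analyst would settle the meaning after the data are in hand.

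The second is the time of the later sample. Tying it to progression or stopping makes both the availability of a value and its timing depend on outcome. CSF is the compartment the correlative background in section 2.4 is built around, and 13.7 gives it no place.

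At stake is whether the biomarker results can be read as evidence about response and about drug effect. No decision rule of the trial depends on them.

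**Working it through.** Section 13.7 states no figure, so there is none to reproduce. The check sets sections against each other and counts scheduled samples.

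**1. Grouping.** Sections 13.1, 13.2 and 13.5 name one primary endpoint, OS3. Section 13.1 lists response as secondary: leptomeningeal, intracranial, and extracranial by RECIST and by irRC. That is 4 response classifications, and 4 + 1 (OS3) = 5 candidate splits. Section 13.6 already provides for cases where RECIST and irRC disagree, so the splits are not interchangeable.

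**2. Group sizes if OS3 were used.** Inputs from 13.2 are 18 evaluable patients and OS3 of 43% or 18%.

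- 18 × 0.43 = 7.74, about 8 alive and 10 not.
- 18 × 0.18 = 3.24, about 3 alive and 15 not.

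The smallest attainable two-sided exact rank-sum p-value is 2/C(18,8) = 2/43,758 = 0.00005, or 2/C(18,3) = 2/816 = 0.0025, so the test can be run. Simulated power follows (assumed: normal markers with equal SD, two-sided 5%, 1,000 data sets per cell):

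| Split | Shift 1.0 SD | 1.5 SD | 2.0 SD |
|---|---|---|---|
| 8 v 10 | 0.45 | 0.81 | 0.96 |
| 3 v 15 | 0.26 | 0.51 | 0.78 |

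The balance of the split largely decides what can be seen, so the choice should not be left open.

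**3. Timing of the later sample.** Treatment has no fixed end (sections 5.1 and 5.5), so a patient still on treatment at analysis has no value yet. Section 11.2.5 allows treatment for up to three months after initial radiographic progression. Progression and discontinuation can therefore be two dates months apart in one patient, and 13.7 does not say which applies. Among patients with a value, time on drug varies from one to the next.

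**4. CSF and blood in the three calendars of section 10.**

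| Calendar | CSF at pre-study and Week 1 | On-treatment CSF (weeks) | CSF at off-study/off-treatment | Blood at that visit |
|---|---|---|---|---|
| Induction | yes | 4, 7, 10 | not marked | marked |
| Maintenance | n/a | 13, 17, 21 | not marked | marked |
| NSCLC/head and neck | yes | 5, 9 | not marked | marked |

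In the first 12 weeks, 3 on-treatment CSF draws (or 2 for NSCLC/head and neck) are scheduled, and the change in 13.7 does not refer to them.

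**5. How near CSF falls to a scan.** Lag = scan week minus the latest scheduled CSF week at or before it. Scans are taken as every 6 or 8 weeks on the calendars' week numbering, with the pattern repeating.

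- Induction, Week 7: 7 − 7 = 0.
- Maintenance, Weeks 13, 21, 29: 0 each.
- NSCLC/head and neck: 7 − 5 = 2, 13 − 13 = 0, 19 − 17 = 2, 25 − 25 = 0, 31 − 29 = 2, 37 − 37 = 0.

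A scheduled draw lies 0 to 2 weeks before a scheduled scan. A patient who stops between visits may have none that close.

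**6. What depends on the faulty pieces.** The two-group baseline comparison needs the grouping. The PFS and OS analyses by baseline marker need neither the grouping nor a later sample. Blood change can be computed for patients who stop and give the sample. Tissue change exists only where a second specimen was taken in clinical care. CSF change has no rule in 13.7.

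**The case against.** The best defence is that the grouping is a slip of wording. Only OS3 is primary, and section 13.2 speaks of patients achieving the primary outcome, so an analyst could simply use it. That is a possible reading, but it compares survivors with non-survivors. In a single arm that reflects prognosis as well as treatment, and objective 1.4 asks about response.

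On timing, 13.7 is headed blood and tissue, and end-of-treatment blood is scheduled. This stands for blood. It does not settle CSF: if CSF falls under 13.7, no draw is marked at the off-study/off-treatment visit; if it falls outside, section 13 gives it no analysis.

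From the blank cells a reader might infer that no CSF will exist near progression. The documents do not support that. Progression is usually found at a scheduled scan, with a CSF draw at or up to two weeks before it, and cytologic progression in 11.4 is itself a CSF finding. Section 13.7 still does not say that the nearest draw may be used.

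A reader might also infer that tissue change is out of reach for most patients. No figure supports this: section 11.2.5 encourages surgery at radiographic progression, section 9.3 provides for tissue from surgery during the trial, and 13.7 makes the tissue-blood correlation subject to data availability. What stands is only that paired tissue is not assured.

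Finally, section 9.2 already plans the on-treatment contrast. True, but it fixes no time point and 13.7 does not take it up.

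**Conclusion.** The point holds. The baseline comparison has no valid grouping as written, with five candidate splits of 18 evaluable patients. The only change that 13.7 defines leaves out patients still on treatment, mixes drug effect with progression and time on drug, and passes over CSF and the on-treatment samples already scheduled.

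A reader might conclude that objective 1.4 cannot be answered. That goes too far. The objective requires no change score, the PFS and OS analyses by baseline marker can be done as written, blood change can be computed for those who stop, and the response comparison becomes valid once the response is named. The objective is weakened.

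The conclusion rests on the calendars as they read here and on open-ended treatment. The documents do not say how many patients would still be on treatment at analysis, so the size of that gap is unknown. The analysis is exploratory and mainly descriptive, and the primary result is unaffected. The section should be corrected, but the trial does not hinge on it.

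**What to change.** Amend section 13.7 before biomarker data are examined against outcome.

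- **(a) Grouping.** Replace the phrase with leptomeningeal response: CR or PR versus SD, PD or not evaluable. State how the cytologic, neurologic and radiographic columns of 11.4 combine, since 11.4 gives no rule. The rule matters: the neurologic PR entry can be met by symptoms that have not worsened, so counting any one column would make many stable patients responders. Say also how patients enrolled on imaging with negative cytology (section 3.1) are classed. Show OS3 status as a separate, labelled split.
- **(b) Main change.** Name CSF as well as blood. Define the change as pre-dose Week 1 to the first scheduled on-treatment sample, for every patient with both: Week 4, or the first 4-weekly sample for NSCLC/head and neck. In that calendar the blood row, as it reads here, shows Week 4, while its footnote gives every 4 weeks after Day 1 and the CSF row shows Week 5. A shifted column in the extracted table may explain this; check and reconcile the two first.
- **(c) Later change.** Keep the change at progression or discontinuation as a separate descriptive summary. State which date applies when the two differ, and report how many patients contribute. Limit tissue change to patients with paired tissue.

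The cost is SAP wording; every blood and CSF sample is already scheduled. The downside is that an early fixed time point says less about resistance at progression, which remains descriptive under (c). Leptomeningeal response is a recommendation based on the disease under study. Another named response would also cure the ambiguity if it is fixed in advance.
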